## **6.2.2. Safety Procedures**

### **6.2.2.1. Physical Examination**

A full physical examination will be performed at the screening visit. At a minimum the following will be assessed: ear, nose and throat, cardiovascular system, pulmonary system, skin, abdomen and neurological system. At all other time points a targeted (symptom directed) examination will be performed at the Investigator's discretion.

### **6.2.2.2. Twelve- Lead Electrocardiogram**

Twelve lead ECGs should be performed at the times outlined in the Time and Events table ([Table 1](#)) in a standardized manner, i.e., after the patient has rested in the semi-supine position for at least 10 minutes. Measurements will be made using an ECG

Study Number: INVEX-CLIN-IIH-301 Protocol	Compound No.: Presendin
	Version: 3.0

machine that automatically calculates the heart rate and measures PR, RR, QRS, and QT intervals.

All ECG traces will be reviewed and signed by the Investigator or designee and any abnormalities will be marked as clinically significant or not clinically significant.

### **6.2.2.3. Vital Signs**

Vital signs, including systolic and diastolic blood pressure and heart rate, will be measured at the time points specified in [Table 1](#).

Patients should rest in a supine position for 10 minutes before the vital signs are assessed. Three recordings will be taken and averaged.

### **6.2.2.4. Laboratory Assessments**

Blood and urine samples will be processed at the site. Routine biochemistry and haematology samples will be evaluated at the trial appointed central laboratory. PK, ADA and CSF samples will be stored at the central laboratory and evaluated at a qualified international laboratory. Details of handling and shipping are described in the Laboratory Manual.

#### **6.2.2.4.1. Haematology**

Blood for the assessment of haematology parameters will be collected at the times outlined in the Time and Events table ([Table 1](#)). The following parameters will be assessed during the trial:

- Total blood count; consisting of:
  - Red blood cells
  - Haematocrit
  - Mean cell volume
  - Mean cell haemoglobin
  - Mean cell haemoglobin concentration
  - Glycated haemoglobin (HbA1C)
  - Blood glucose (non-fasting)
  - Platelets
  - White blood cells

Study Number: INVEX-CLIN-IIH-301	Compound No.: Presendin
Protocol	Version: 3.0

- Neutrophils
- Lymphocytes
- Monocytes
- Eosinophils
- Coagulation (prothrombin time, international normalised ratio, activated partial thromboplastin time, thrombin time, fibrinogen)
- Basophils

#### **6.2.2.4.2. Clinical Chemistry**

Blood for the assessment of clinical chemistry parameters will be collected at the times outlined in the Time and Events table ([Table 1](#)). The following parameters will be assessed during the trial:

- Sodium
- Potassium
- Chloride
- Bicarbonate
- Blood urea nitrogen
- Creatinine
- Total bilirubin
- Total protein
- Albumin
- Alanine transaminase
- Aspartate aminotransferase
- Alkaline phosphatase

#### **6.2.2.4.3. Urinalysis**

Urine samples will be collected at the times outlined in the Time and Events table ([Table 1](#)). The following parameters will be assessed at each time point:

- Glucose
- Ketones

Study Number: INVEX-CLIN-IIH-301	Compound No.: Presendin
Protocol	Version: 3.0

- Specific gravity
- Blood
- pH
- Protein
- Urobilinogen

#### **6.2.2.4.4. CSF**

CSF sample from visit 10 LP will be retained for future potential analysis of disease and drug related biomarkers.

#### **6.2.2.4.5. Pregnancy**

At screening blood will be collected to enable a serum pregnancy test to be performed. At visits thereafter, urine will be collected from female patients of childbearing potential at the times outlined in the Time and Events table ([Table 1](#)) to enable highly sensitive urine-based pregnancy tests to be performed. Female patients who are identified as being pregnant during the trial will be withdrawn from further treatment but will continue to attend safety follow-up visits.

The Investigator or designee should report any pregnancies in female patients to the Sponsor or designee, using the Pregnancy Report Form, within 24 hours. The contact details for reporting are:

[REDACTED]

Female patients or partners of patients who become pregnant should be followed until delivery, stillbirth or termination. The outcome of the pregnancy and, if applicable, the health of the baby, should be reported to the Sponsor using the Pregnancy Report Form.

#### **6.2.2.4.6. Pharmacokinetic sampling**

Pharmacokinetic sampling is to characterize the pharmacokinetics of exenatide after once weekly subcutaneous administration of Presendin at the times outlined in the Time and Events table ([Table 1](#)).

The primary purpose of the pharmacokinetic sampling is to characterize the steady state concentrations of exenatide. All actual sampling times and dosing times will be recorded.

Sampling and processing will be performed as described in the Laboratory Manual.

Study Number: INVEX-CLIN-IIH-301 Protocol	Compound No.: Presendin Version: 3.0
---	--

#### **6.2.2.4.7. Anti-drug Antibodies sampling**

Anti-drug antibodies sampling will be performed in all subjects at the times outlined in the Time and Events table ([Table 1](#)).

Sampling and processing will be performed as described in the Laboratory Manual.

#### **6.2.2.5. Adverse Events**

Patients will be asked non-leading questions to assess how they are feeling at each clinic visit. Adverse events will be assessed and reported as outlined in Section [12](#).

### **6.3. Efficacy Procedures**

#### **6.3.1. Intracranial Pressure**

Assessment of ICP will be measured by LP in the lateral decubitus position. The diagnostic LP is performed by the clinical team prior to recruitment and the measurement must be made from the lateral decubitus position. The research LP will be performed according to LP standard operating procedure (SOP). Lumbar puncture will ideally be performed after visual assessments as outlined in the Time and Events table ([Table 1](#)).

In some cases the lumbar puncture might be conducted using imaging guidance according to the preference of the individual and site. This could be using x-rays, computer tomography or ultrasound guidance.

Any additional LP procedures, outside of the protocol would constitute a protocol deviation and ideally should be discussed with the Investigator before the procedure is performed.

Non-protocol LPs should be recorded in the Case Report Form.

#### **6.3.2. Visual Assessments**

Visual assessments should be performed on both eyes. All visual assessments should be uploaded without delay on the day of the visit to the OCT and Visual Field Reading Centres. In all cases the site is responsible for initial checks of the clinical data in the wider context of the patient's disease, as well as a data quality check.

##### **6.3.2.1. Frisén grade**

At Screening (visit 1) Frisén grading (0 – 5) should initially be performed at the site through a dilated pupil. The presence of papilloedema will be verified by the OCT Reading Centre at screening (visit 1) and a report sent to the site. During screening,

Study Number: INVEX-CLIN-IIH-301 Protocol	Compound No.: Presendin
	Version: 3.0

where there is uncertainty regarding the presence of papilloedema and / or Frisén grade a fundus photo and or ultrasound scan (B scan) of the optic nerve may be conducted (or may be requested by the OCT Reading Centre) and if uncertainty persists evaluated by the IAC.

At Baseline (visit 2) sites will reconfirm the Frisén grade

### **6.3.2.2. Optical Coherence Tomography**

Imaging may be acquired using Heidelberg Engineering or Cirrus platforms according to the OCT SOP. Key measures are RNFL, optic nerve head size, and macular ganglion cell layer/complex thickness..

- Sites should initially check the clinical interpretation of the OCT scan and scan quality. The OCT should then go through the upload processes to the OCT Reading Centre. The OCT will then be reviewed by the OCT Reading Centre for a full quality assessment. The report from the OCT Reading Centre will then be sent to the site. Where the OCT is of insufficient quality, it should be repeated as soon as possible. Where the OCT has not been processed correctly at the site the processing should be re-performed as soon as possible thereafter. Repeated or reprocessed images would then be again transmitted to the OCT Reading Centre for a full assessment.
- If the site is concerned with the OCT findings, suggesting that the patient is a potential treatment failure and may require rescue therapy, the OCT Reading Centre review will be prioritised and when indicated expedited to the IAC.

### **6.3.2.3. Humphrey Visual Field**

The visual field will be measured by Humphrey Visual Field analysis (24-2 SITA-Standard) including standardised refraction as indicated, according to the Visual Field Centre SOP (Manual of Procedures).

- At screening HVF will be reviewed by the Visual Field Reading Centre to confirm eligibility.
- Inability to perform a reliable visual field examination as deemed by the Visual Field Reading Centre in study eyes (including >15% false positives), is an exclusion criterion. HVF can be repeated to obtain as assessment with reliable performance.
- If the site is concerned with the HVF findings, suggesting that the patient is a treatment failure and may require rescue therapy, the Visual Field Reading Centre review will be prioritised and when indicated expedited to the IAC.

Study Number: INVEX-CLIN-IIH-301	Compound No.: Presendin
Protocol	Version: 3.0

#### **6.3.2.4. Visual Acuity**

Assessment of visual acuity will be recorded using a LogMAR chart (unaided, best corrected, and with pin hole).

#### **6.3.3. Headache Assessments**

Patients will be provided with an electronic/paper diary at screening to complete during the trial. Information collected will be used to assess the following headache parameters:

- Monthly headache days
- Monthly moderate to severe headache days
- Responder rate
- Monthly acute analgesic use
- Headache severity (11-point NRS)

##### **6.3.3.1. Headache Preventative Medication Review**

A review of any headache preventative medications taken by the patient will be undertaken at each clinic visit. If the Investigator alters the headache preventative medication, this will be considered rescue medication (Section 10.1.1) and the IAC consulted. Use of headache preventative medication will be recorded at trial visits as outlined in the Time and Events table (Table 1).

Patients will record their acute headache analgesic use in their trial diary.

#### **6.3.4. Patient Reported Outcomes**

##### **6.3.4.1. Visual related**

Assessment of visual related quality of life will be derived from self-reported responses to the VFQ-25-10 item supp (see Section 16.5 Appendix 5).

##### **6.3.4.2. Health-related**

Assessment of health-related quality of life will be derived from self-reported responses using the following questionnaires:

- 36-item short form survey
- EuroQol -5 dimension -5 level survey

Study Number: INVEX-CLIN-IIH-301 Protocol	Compound No.: Presendin
	Version: 3.0

A Healthcare Utilisation Form will be completed by the trial site staff at clinic visits.

All questionnaires can be found in Section 16, Appendix 2 for SF-36 and Appendix 3 for the EuroQoL- 5D-5L survey.

#### **6.3.4.3. Headache related Quality of Life**

Assessment of headache-related quality of life will be derived from self-reported responses to the Headache Impact Test-6 questionnaire and performed at time points as outlined in the Time and Events table (Table 1). A copy of this questionnaire can be found in Section 16.4, Appendix 4.

#### **6.3.4.4. Patient Global Impression of Change**

The Patient Global Impression of Change will be conducted at visit 10, as outlined in the Time and Events table (Table 1).

It is a single item questionnaire using a seven-point verbal response scale to assess overall change in the patient's status since taking trial medication. A copy of this questionnaire can be found in Section 16.6, Appendix 6

#### **6.3.5. Body Weight and Body Mass Index**

The patient's body weight and BMI will be measured at the time points as outlined in the Time and Events table (Table 1).

The patient's height will be measured at Screening (shoes off).

Study Number: INVEX-CLIN-IIH-301 Protocol	Compound No.: Presendin Version: 3.0
---	--

## 7. SAFETY MEASURES DUE TO A GLOBAL CRISIS

The COVID-19 global pandemic presents numerous challenges to the conduct of ongoing clinical trials. In line with the FDA and European Medicines Agency's Guidance on the Management of Clinical Trials During the COVID-19 (Coronavirus) Pandemic (EMA, 2021), the following protocol considerations are provided to ensure patients safety is maintained and adequate benefit/risk analyses are applied relative to the completion of study procedures and maintaining the investigational product supply chain. Other unforeseen global crises may occur during the conduct of the study, similar to the COVID-19 global pandemic, in which case the following protocol considerations may also be applied.

Recognizing the flexibility required to manage the impact of the pandemic (or other global crisis) on this clinical study, additional details will be added to respective study manuals, project plan documents, and communicated to the investigative sites as needed. For any additional questions, the investigator should confer with the sponsor.

### Number of Trial Patients

The evolving situation of the pandemic (or other global crisis) may result in a substantial number of patients' early withdrawal from the study, which could affect the data integrity of the study. Because of this risk, the sponsor may decide to recruit additional patients in the study, beyond the expected number, to mitigate such risk.

### Study Visits

There are a number of on-site visits that would be required to ensure study validity. If there are local travel restrictions, isolation requirements, or the investigator determines it to be unsafe for patients to attend their scheduled study visits, the site staff may conduct certain visits via telemedicine (phone or video calls) to minimize patient risk as follows.

### *Screening Period*

The following visit must be performed in person:

- Screening/Visit 1

Note: To minimize direct, in-person contact between site personnel and patients, certain screening procedures may be performed remotely via telemedicine. All other procedures should be done in-person while the subject is on-site.

Specifically, the following procedures may be done remotely:

- Informed consent (where applicable, per approved IRB/IEC process)
- Demography

Study Number: INVEX-CLIN-IIH-301 Protocol	Compound No.: Presendin
	Version: 3.0

- Medical and ophthalmic history
- Concomitant medication history
- Headache history
- Headache preventative medication review
- Train and dispense headache diary
- Trial medication training

*Randomised period*

- Baseline (Visit 2)

There are essential aspects to the baseline visit which must be performed in person.

If the baseline visit is delayed the headache diary should utilise the preceding 7 days data. Where the visit is delayed by more than 10 days due to a global crisis the patient will be considered to have failed screening. Patients who screen failed due to the pandemic (or other global crisis) may be rescreened at a later time, if feasible.

To minimize direct, in-person contact between site personnel and patients, certain procedures may be performed remotely via telemedicine. All other procedures should be done in-person while the subject is on-site. Specifically, the following procedures may be done remotely:

- Concomitant medication review
- Headache preventative medication review
- Headache diary review
- Adverse events
- Patient reported outcomes
- Health utilisation form

- Visit 4, 5, 6, 7, and 8

There are essential aspects to these visits which must be performed in person.

Where this is not possible due to the pandemic or other global crisis the following components of the visit should be performed at the next available opportunity in line with the schedule of assessments table:

- Vital signs
- Body weight and BMI
- Physical examination

Study Number: INVEX-CLIN-IIH-301	Compound No.: Presendin
Protocol	Version: 3.0

- Urine pregnancy test
- Electrocardiogram
- Optical coherence tomography imaging
- Humphrey Visual Field
- Visual acuity testing
- Laboratory assessments
- Pharmacokinetic sampling
- Anti-drug antibodies sampling

To minimize direct, in-person contact between site personnel and patients, certain procedures may be performed remotely via telemedicine. All other procedures should be done in-person while the subject is on-site. Specifically, the following procedures may be done remotely:

- Concomitant medication review
- Headache preventative medication review
- Headache diary review
- Adverse events
- Patient reported outcomes
- Health utilisation form

- **Visit 10**

There are essential aspects to these visits which must be performed in person. Where this is not possible due to the pandemic or other global crisis the following components of the visit should be performed at the next available opportunity in line with the schedule of assessments table:

- Vital signs
- Body weight and BMI
- Physical examination
- Urine pregnancy test
- Electrocardiogram
- Optical coherence tomography imaging
- Humphrey Visual Field
- Visual acuity testing
- Laboratory assessments
- Pharmacokinetic sampling
- Anti-drug antibodies sampling

Study Number: INVEX-CLIN-IIH-301 Protocol	Compound No.: Presendin
	Version: 3.0

- Lumbar puncture\*

\* Lumbar puncture to be ideally performed after visual assessments. In the 4 weeks prior to visit 10, patients must not have missed more than one dose of trial medication and must have self-administered their final dose within 7 days of visit 10. Patients will be reminded by the trial site to self-administer trial medication weekly, to continue this until the completion of visit 10 and to bring their trial medication with them at visit 10 for return.

Where more than one dose has been missed during the preceding 4 weeks, visit 10 should be delayed. Self-administration of trial medication should continue at 7-day intervals and then visit 10 rescheduled to ensure no more than one dose of the trial medication has been missed in the previous 4 weeks. Visit 10 should be delayed no more than 14 days, if possible, but this can be extended according to local government policy if a patient is unable to attend (for example if a patient is self-isolating) as long as medication use is maintained as above.

- Follow up/ Visit 11

This should be performed as a telephone visit unless clinical contact is necessary, as per protocol. Where face to face contact is required, this should be conducted at the earliest available opportunity.

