	V1 Clinic	V2 Clinic Baseline	V3 TC	V4 Clinic	V5 Clinic	V6 Clinic	V7 Clinic	V8 Clinic	V9 Clinic	V10  Clinic		Unscheduled repeat visual assessments 
Visit Window (days)		+3	± 1	± 3	± 3	± 5	± 5	± 5	± 5	± 14		± 5
Month	0	0			1	2	3	4	5	6		
Week	-1	0		2	4	8	12	16	20	24		29
Day	-7	1	3	15	29	57	85	113	141	169		204
Pharmacokinetic (PK) sampling 		X 		X	X	X	X	X	X	X		
Anti-Drug Antibodies (ADA) sampling		X		X	X	X	X	X	X	X		
Lumbar Puncture 										X 		
Trial medication training 	X	X										
Randomisation		X										
Trial medication Dispensing	X	X			X	X	X	X	X			
Trial medication Accountability				X	X	X	X	X	X	X		

 The screening period must be a minimum of 7 days, up to a maximum of 10 days. Patients who do not meet the eligibility criteria based on diary review at randomisation/baseline (e.g., too few headache days or unacceptable concomitant medication use) will be considered screen failures; however, if the patient wishes and the Investigator is in agreement, he/she can be re-screened as a new patient. If the screening period exceeds 7 days, then eligibility will be based on the last 7 days of the screening period, i.e., the 7 days prior to randomisation visit. Trial site research team should review diaries remotely on a weekly basis to ensure compliance and follow up any patients with missing data

 Vital signs to include: blood pressure and heart rate

 Women of child-bearing potential. Serum pregnancy test to be conducted at screening, thereafter, highly sensitive urine pregnancy tests will be conducted. Visit 11 urine pregnancy test may be conducted at home

 Frisén grade will be evaluated locally and the presence of papilloedema verified by the OCT Reading Centre at screening to confirm eligibility. Indeterminate cases should be referred to the IAC (and supplemented with fundus photography and ultrasound scan of the optic nerve) to confirm papilloedema prior to randomisation visit

 Haematology, coagulation, biochemistry and urinalysis

 All actual sampling times and dosing times will be recorded

 Baseline Post-dose PK blood sample

Study Number: INVEX-CLIN-IIH-301 Protocol	Compound No.: Presendin
	Version: 3.0

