### **6.1.4. Visits 4, 5, 6, 7, 8 and 9 Clinic visits**

- Concomitant medication review
- Headache preventative medication review
- Headache diary review
- Vital signs (triplicate readings for blood pressure and heart rate will be taken at 1-minute intervals)
- Body weight and BMI (not visit 4)
- Adverse event review
- Targeted physical examination (visit 6, 8 and 9 only)
- Urine pregnancy test for women of child-bearing potential
- Electrocardiogram
- Visual Assessments to both eyes
  - Optical coherence tomography Imaging
    - Sites should initially check the scan quality. The OCT scan should then go through the upload processes to the OCT Reading Centre, without delay. The OCT scan will then be reviewed by the OCT Reading Centre for a full quality assessment. The report from the OCT Reading Centre will be sent to the site. Where the OCT is of insufficient quality it should be repeated as soon as possible at an unscheduled visit. Where the OCT processing is of insufficient quality it should be reprocessed as soon as possible by the site.

Study Number: INVEX-CLIN-IIH-301 Protocol	Compound No.: Presendin
	Version: 3.0

- Humphrey Visual Field (24-2 SITA-Standard)
  - Sites should initially check the performance quality of the HVF (to ensure no more than 15% false positives). The HVF should then be uploaded to the Visual Field Reading Centre without delay (an initial quality assessment takes place during the upload procedure). The HVF will then be reviewed by the Visual Field Reading Centre for a full quality assessment. The report from the Visual Field Reading Centre will be received by the site. Where the visual field is of insufficient quality it should be repeated at an unscheduled visit without delay.
- Visual Acuity (LogMAR score)
- Patient reported outcomes: VFQ-25 & 10-item supp, HIT-6, SF-36 and EQ-5D-5L in diary (not visit 4)
- Health Utilisation Form
- Laboratory assessments
- Pharmacokinetic blood sampling
- Anti-Drug Antibodies blood sampling
- Trial medication dispensing (not Visit 4) and accountability - patients should be reminded by the trial site to self-administer the trial medication weekly and to return used and unused trial medication at clinic visits

### 6.1.5. Visit 10

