#### **6.1.6. Visit 11 Follow-Up**

This visit will be performed as a telephone call to conduct headache preventative medication review and check for any AEs or changes in medication. In the event of any abnormal safety assessments identified at the end of treatment, e.g., abnormal ECG, abnormal routine laboratory results or ongoing adverse events, this visit may be performed at the clinic to repeat or follow up safety assessments.

A urine pregnancy test (for women of childbearing potential) will be performed, this can be conducted at home if the visit is performed by telephone call.

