### **Study Drug Dispensation and Distribution**

If a patient is not able to attend a clinic visit, to ensure the continuity of providing patients' study drug within the constraints imposed by the pandemic (or other global crisis), the site staff may decide to supply study drug to patient as follows:

- Adequate supplies of study drug can be shipped to the patient by the study staff using a third-party service with approval from the patient. The third-party vendor will be agreed upon with the sponsor.
- The patient may request, with prior arrangement/agreement with the site, an authorized individual (a relative or delegate) to retrieve the study drug from the study site if the patient is unable to personally to do so.

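### Protocol v3.0, Section 7: the urine pregnancy test is deferred at crisis-missed Visits 4–8 and 10 and Visit 9 is left out, while drug can be supplied without it (minor)

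*Protocol*

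**What the plan says.** All references are to version 3.0 unless stated.

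- **Deferral.** Section 7, Visits 4, 5, 6, 7 and 8: where in-person attendance is impossible, "the following components of the visit should be performed at the next available opportunity in line with the schedule of assessments table". The list includes the urine pregnancy test. The Visit 10 block repeats the rule and the test. Visit 9 appears in neither block.
- **Remote procedures.** For Visits 4–8 these are medication and diary reviews, adverse events, questionnaires and the health utilisation form. The pregnancy test is not among them, and "All other procedures should be done in-person while the subject is on-site".
- **Supply.** If a clinic visit is missed, "Adequate supplies of study drug can be shipped to the patient by the study staff using a third-party service", or an authorised relative or delegate may collect it. No pregnancy test is mentioned.
- **Routine schedule.** Section 6.1.4 has the urine test at each of Visits 4–9 and lists "Trial medication dispensing (not Visit 4) and accountability". Table 1 agrees: drug is dispensed at Visits 5–9 and not at Visits 4 or 10.
- **Home testing.** Table 1, footnote 3: "Visit 11 urine pregnancy test may be conducted at home". Section 6.1.6 agrees: "this can be conducted at home if the visit is performed by telephone call".
- **General clause.** Section 7, under direct contracts with third parties, asks that safety data obtainable locally be gathered at a remote visit, if need be through local practitioners.

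**The concern.** In routine conduct the pregnancy test and the next drug supply fall at the same visit. Section 7 separates them: supply may continue by courier or delegate while the test waits. A site that follows the specific lists can therefore keep a woman of childbearing potential on weekly dosing past her scheduled test. That test is one route to the withdrawal from treatment that Sections 6.2.2.4.5 and 11.2.1 require in pregnancy, and Section 1.1.2 reports foetal toxicity of Byetta in animals at three times the human exposure.

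The OCT, perimetry and ECG on the same deferral list need site equipment. The protocol itself accepts a urine test done at home, but only at Visit 11, after treatment has ended.

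**Working it through.** The plan states no figure on this point, so there is none to reproduce. The check sets the texts side by side and works from Table 1's visit days.

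**Texts**

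| Visit | Test scheduled | Drug dispensed | Section 7 rule for the test |
|---|---|---|---|
| 4 | yes | no | deferred |
| 5–8 | yes | yes | deferred |
| 9 | yes | yes | none |
| 10 | yes | no | deferred |

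The supply paragraph is not limited by visit, so it also reaches drug due at Visit 9.

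**Inputs.** Visit days: V2 = 1, V4 = 15, V5 = 29, V6 = 57, V7 = 85, V8 = 113, V9 = 141, V10 = 169. Windows: ±3 days at V5, ±5 at V6–V9, ±14 at V10.

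**Routine intervals.** From V5 on, the nominal gap is 28 days (for example 57 − 29). With windows, compliant gaps reach:
- V5 to V6: 28 + 3 + 5 = 36 days
- V6 to V7, V7 to V8, V8 to V9: 28 + 5 + 5 = 38 days
- V9 to V10: 28 + 5 + 14 = 47 days

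**One missed visit, test left until the next scheduled visit (nominal days)**
- Missed V6: 85 − 29 = 56
- Missed V7: 113 − 57 = 56
- Missed V8: 141 − 85 = 56
- Missed V5: 57 − 15 = 42
- Missed V4: 29 − 1 = 28, no more than the routine interval

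A test done d days late gives 28 + d days. At d = 7 this is 35 days, inside the routine window. At d = 14 it is 42, and at d = 28 it is 56, which is 28/7 = 4 further weekly doses before the test. Applying windows to both sides leaves the last excess unchanged: missed V6 gives at most 56 + 3 + 5 = 64 days against 36, still 28 more.

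No figure is claimed for Visit 10. It has no dispensing, and a 14-day delay is already within its window.

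**Expected events.** Take all 120 active-arm patients as of childbearing potential, 28 extra days each, and the protocol's contraception standard of under 1% failure per year:
- Every patient misses one visit: 120 × 28/365.25 = 9.2 patient-years; 9.2 × 0.01 = 0.092, so under 0.1.
- 10% miss one visit (an assumption; the protocol gives no missed-visit rate): 0.92 × 0.01 = 0.0092, so under 0.01.

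**The case against.** The strongest reply is that Section 7 already contains the answer. The pregnancy test sits under Safety Procedures (6.2.2.4.5), and a urine test is plainly safety data obtainable locally, so the general clause could be read as calling for it. The remote list concerns telemedicine, "the site staff may conduct certain visits via telemedicine (phone or video calls) to minimize patient risk as follows", so absence from that list is no prohibition. Section 7 also says that "additional details will be added to respective study manuals, project plan documents, and communicated to the investigative sites as needed". This has force. It means the deferral is opposed by a general rule. It does not remove the conflict: neither clause names the test or amends the lists that do name it, and a site is left with a specific instruction to defer and a general one to collect.

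Other replies reduce the size of the point:

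- Section 6.1 says a visit missed through self-isolation is held at the earliest opportunity, which covers Visit 9 in that case, though not in other crises.
- The visit windows absorb short deferrals, as shown above.
- Contraception, the duty to report pregnancy immediately (12.3) and remote adverse-event review all continue.
- Shipment is at the site's discretion.
- Routine dispensing sets no negative-test condition either, so supply without a test breaks no stated rule.

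Finally, version 4.0 exists and its body is not shown, so whether the wording is still in force cannot be checked.

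**Conclusion.** The wording conflict in version 3.0 is real, and its consequence is small. The deferral lists pull against both the general safety-data clause and the home test accepted at Visit 11, and Visit 9 has no crisis rule. For a single missed Visit 6, 7 or 8 the nominal test interval could double to 56 days at most; for Visit 5 it could reach 42; for Visit 4 there is no excess. Expected extra exposed pregnancies are under 0.1 in the active arm even if everyone missed one visit. No endpoint, power or error rate is affected. Severity is minor.

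Three stronger readings are tempting and not supported:

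- **That the protocol waives the test for shipped drug.** The supply paragraph is silent on the test; silence is not a waiver.
- **That gaps of several months are to be expected.** If Visits 5–8 were all missed and the test waited for Visit 9, the gap would be 141 − 15 = 126 days. That assumes no opportunity arose in between, whereas the text asks for the next available one.
- **That Section 7 was overlooked when the Visit 11 test was added.** Version 1.0 has the same deferral lists and no Visit 11 test, but Section 7 was edited elsewhere between versions (the lumbar puncture note) and version 2.0 is not shown. Oversight is only an inference.

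**What to change.** First check whether the version 4.0 body keeps this wording. If it does, in Section 7:

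1. Remove the urine pregnancy test from the deferral lists for Visits 4–8 and Visit 10.
2. Add Visit 9 to the crisis rules.
3. State that when any of Visits 4–10 scheduled in clinic is not held in person, the urine test is done at home or locally at the scheduled time, as Table 1 footnote 3 already allows at Visit 11.
4. Send a kit with each drug shipment or collection. For Visits 4 and 10, which dispense nothing, supply it at the preceding visit or shipment.

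Whether supply should wait for a negative result is a question for the sponsor's clinicians. The cost is a short wording change and home kits for women of childbearing potential at crisis-missed visits; the test itself is already scheduled. The longest nominal interval then stays at 28 days.
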